6.6 Survival Follow-up

Survival data will be collected via telephone or clinic visits every 3 months (± 10 days) from the date of last treatment (date of last treatment is calculated from the last dose of trametinib) until death, loss to follow-up, withdrawal of consent, study termination by the Sponsor, or up to 5 years. In addition, any new anti-cancer therapies and procedures should be collected and documented. Should subjects refuse or drop out of survival follow-up, attempts should be made to obtain any death information via public records whenever possible.

6.7 Schedule of Assessments Summary

Procedure	Screening	Cycle 1 ⁴			Cycle 2 ⁴			Additional cycle ⁴			Every 12 weeks or sooner, at the discretion of the physician	End of Treatment (EoT) ⁸	Survival Follow-up ¹²
		Wk 1	Wk 2	Wk 3	Wk 1	Wk 2	Wk 3	Wk 1	Wk 2	Wk 3			
Informed Consent	X												
Medical History	X												
Demographics	X												
Physical Exam	X	X	X		X	X		X				X	
Vital Signs	X	X			X			X				X	
ECOG PS	X	X			X			X				X	
CBC	X	X			X			X				X	
Serum Chemistry ¹³	X	X			X			X				X	
Tumor Biopsy	X												
	X												

CONFIDENTIAL

This material is the property of the NYU School of Medicine and Langone Medical Center. Do not disclose or use except as authorized in writing by the study sponsor

Baseline imaging within 4 weeks prior to enrollment (CT/PET-CT/MRI)													
Pregnancy Test (Urine)	X	X			X			X					
EKG	X	X ₁₁			X ₁₁			X ₁₁					
Archived tumor	X												
Fresh Core Biopsy	X ₂		X ₃	X ₃								X	
Pharmacokinetic blood samples		X ₁₀	X		X ₁₀	X		X				X	
Immunogenicity sample		X			X							X	
Concomitant meds	X	X	X		X			X				X	
CDX-3379 dosing ¹⁶		X			X			X					
Trametinib dosing		X	X	X	X	X	X	X	X	X			
AE assessment and reporting		X	X		X			X				X	
Disease evaluations ^{5,7}	X										X ₉	X ₁	
Overall Survival Reporting ⁶													X
Echocardiogram/MUGA ¹⁵	X										X		
Ophthalmologic Exam ¹⁴	X	X			X			X					

Footnotes:

- 1 = Unless performed in the prior 6 weeks as part of a previous visit
- 2= prior to first treatment with CDX-3379 and trametinib
- 3= performed between days 14-16
- 4= All procedures should occur ±2 calendar days from scheduled date of visit
- 5 = Disease evaluation per RECIST version 1.1.
- 6 = Should patients refuse or drop out of survival follow-up, attempts should be made to obtain any death information available via public records.
- 7 = Upon disease progression determination
- 8 = End of treatment visit should be completed within 4 weeks of the last dose of study drug
- 9 = end of treatment biopsy/disease progression. Should occur within 4 weeks of last treatment.
- 10 = PK blood samples are collected predose before CDX-3379, immediately following CDX-3379 infusion, and 1 hour post dose following trametinib
- 11= one reading prior to the start of CDX_3379 infusion
- 12= Survival data will be collected via telephone or clinic visits every 3 months (±10 days) from the date of last treatment until death, loss to follow-up, withdrawal of consent, or study termination by the Sponsor
- 13= Comprehensive metabolic panel (sodium, potassium, chloride, carbon dioxide, blood urea nitrogen, creatinine, glucose, calcium, protein total, albumin, AST, ATL, alkaline phosphatase and total bilirubin), LDH, magnesium, and phosphorus.

CONFIDENTIAL

14 = With hand held Ophthalmoscope. Patients will also be asked about eye symptoms at each visit. A formal ophthalmologic examination will be performed as per standard of care if patients develop signs or symptoms of ocular toxicity.

15= ECHO/MUGA should be performed every 12 weeks, or at the discretion of the physician.

16= Pre and post infusion vitals (HR, Blood pressure, O2 sat, temperature) will be taken prior to infusion +/-15 minutes, 30 minutes into the infusion +/- 5 mins, at the end of the infusion (which is 60 minutes) +/- 15 minutes, and 60 minutes after the infusion has finished +/- 15 minutes

7 Statistical Plan

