1.6.1.2.1 Management of Toxicity Related to Trametinib

CONFIDENTIAL

This material is the property of the NYU School of Medicine and Langone Medical Center. Do not disclose or use except as authorized in writing by the study sponsor

Table 1. Recommended Dose Modifications for Trametinib

Target Organ	Adverse Reaction^a	Dose Modification
Cutaneous	Grade 2 rash (tolerable)	Continue treatment and monitor
	Intolerable Grade 2 rash or Grade 3 or 4 rash	Withhold Trametinib for up to 3 weeks If improved within 3 weeks, resume Trametinib at a lower dose (reduced by 0.5 mg) or discontinue Trametinib in patients taking Trametinib 1 mg daily
	Intolerable Grade 2 or Grade 3 or 4 rash that does not improve within 3 weeks despite interruption of Trametinib dosing	Permanently discontinue Trametinib
Cardiac	Asymptomatic, absolute decrease in LVEF of 10% or greater from baseline and is below institutional lower limits of normal (LLN) from pretreatment value	Withhold Trametinib for up to 4 weeks. If improved within 4 weeks, resume Trametinib at a lower dose (reduced by 0.5 mg) or discontinue Trametinib in patients taking Trametinib 1 mg daily
	
 - Symptomatic congestive heart failure - Absolute decrease in LVEF of greater than 20% from baseline that is below LLN - Absolute decrease in LVEF of 10% or greater from baseline and is below LLN that does not improve to normal LVEF value within 4 weeks following interruption of Trametinib 	Permanently discontinue Trametinib
Ocular	Grade 2-3 retinal pigment epithelial detachments (RPED)	Withhold Trametinib for up to 3 weeks. If improved to ≤ Grade 1 within 3 weeks, resume Trametinib at a lower dose (reduced by 0.5 mg) or discontinue Trametinib in patients taking Trametinib 1 mg daily. If it does not improve to ≤ Grade 1 within 3 weeks, discontinue Trametinib.

CONFIDENTIAL

Ocular	Retinal Vein Occlusion	Permanently discontinue Trametinib
Pulmonary	Interstitial lung disease/pneumonitis	Permanently discontinue Trametinib
Other	Intolerable Grade 2 adverse reaction Grade 3 adverse reaction	Withhold Trametinib for up to 3 weeks. If Grade 3 adverse reaction improves to \leq Grade 1 following interruption of Trametinib within 3 weeks then reduce dose of Trametinib by 0.5mg or discontinue Trametinib in patients taking Trametinib 1 mg daily.

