No of pts	Cohort Level	CDX-3379	Trametinib
6	1	15mg/kg IV Q 3wks	2mg daily
6	-1A	15mg/kg IV Q 3wks	1.5mg daily
6	-1B	10 mg/kg IV Q 3wks	1.5mg daily
6	-2A	10mg/kg IV Q 3wks	1.0 mg daily
6	-2B	5 mg/kg IV Q 3wks	1.0mg daily

Safety has been established for the combination of CDX-3379 (ERBB3 antibody) and chemotherapeutic agents and targeted therapy at the standard doses with maximum dose of 20mg/kg. In addition, the recommended treatment dose of trametinib is 2mg. However, no data is available for the combination of CDX-3379 (ERBB3 antibody) and trametinib. In Phase Ib, all patients will start treatment at the cohort 1 doses. Six patients will be enrolled at this dose level and monitored for DLTs for 6 weeks (which is two treatment cycles (42 days)).

[figure not shown]
In these six participants, if none or one subject experiences a DLT, then dose cohort 1 will be considered the RP2D, and phase II of the clinical trial will proceed. After the first 20 patients are enrolled in the initial cohort, enrollment will be placed on hold to monitor for toxicity. At this point, a stopping rule for the cohort expansion portion of the trial for excessive toxicity such that if $\geq 30\%$ of patients enrolled across groups discontinue treatment due to toxicity, enrollment will pause and an assessment of the toxicity of the treatment regimen(s) will be performed. This assessment, along with justification for resumption of enrollment, should be submitted to FDA. This stopping rule for the cohort expansion portion of the trial for excessive toxicity applies regardless of which dose is selected as the RP2D. Toxicities will be reviewed by study sponsor (NYU Langone Health) and DSMC. If $\leq 33\%$ of patients experience DLT based on review, then the study will continue enrollment. If $> 33\%$ of patients experience a DLT, then the study sponsor (NYU Langone Health), DSMC will convene to determine the best course of action (i.e. enrollment at decreased dosing cohort, etc).

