If two or more of the six subjects experience DLT, we will consider the initial dose cohort beyond the MTD and we will enroll six more patients in cohort 1A or 1B, based on the toxicity pattern observed that is felt to be attributed to a particular drug. Dose reduction to -1A or -2A is specifically for toxicity related to trametinib, LVEF reduction, RPED, pneumonitis and LFT abnormalities. -1A is the first reduction, followed by -2A as the second reduction. For all other observed toxicities the default dose-reduced cohort is -1B followed by -2B. In the new dose cohort, if none or one patient experiences a DLT, then the study will open to full enrollment on the Phase II portion of the trial. If two or more of these additional six patients experience DLT, we will then enroll six

CONFIDENTIAL

additional patients at additional dose de-escalation cohorts, to be determined by sponsor (NYULMC) and NYU DSMC), again based on toxicity pattern observed and drug attribution. If two or more patients experience DLT at this new dose cohort, then the trial will be terminated.

Phase 2: There are two Arms - Arm A (*NRAS* mutant melanoma patients) and Arm B (WT melanoma patients). This is the first part of a Simon Minimax design. Each arm will initially enroll 19 subjects. If there are three or fewer responses, then accrual to that cohort will be stopped. Otherwise, the study will be amended to enroll a total of 36 subjects to each approved arm/cohort.

Abbreviations: C = cycle; D = day; PD = progressive disease.

Figure 2: Phase II study design

Translational Research -

We will perform biopsies on all phase Ib patients (expected 6 patients, but could be up to 18) and five patients on each Arm of the study for Phase II. Biopsies will be obtained pre-treatment, on-treatment between day 14-16, and at the time of disease progression. Archival tissue will also be collected. We will investigate pathway inhibition of ERBB3 signaling and MAPK signaling pathways by analyzing components of the signaling pathways in addition to key components integral in these signaling pathways. We will also evaluate NRG1/HRG1 (neuregulin 1/heregulin 1, ERBB3 ligand) expression and correlate this with treatment response.

CONFIDENTIAL

This material is the property of the NYU School of Medicine and Langone Medical Center. Do not disclose or use except as authorized in writing by the study sponsor

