3.5 Primary Safety Endpoints

Safety assessments will consist of monitoring and recording all adverse events, including serious adverse events as well as blood monitoring of hematologic and chemistry values with each cycle of therapy. Patients will also be clinically assessed with regular monitoring of vital signs and physical exam. The secondary endpoints of the phase Ib portion of the study includes adverse event rates. Refer to Section 8 for further information on safety monitoring.

Determination of final MTD/RP2D will be guided by the incidence of drug-related side effects and dose de-escalations occurring within 6 weeks (two cycles) which allows for substantial amount of time for unexpected toxicities with combination of CDX-3379 with trametinib. This is detailed in section 3.1.

CONFIDENTIAL

4 Subject Enrollment and Withdrawal

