6.1 Visit 1 – Screening

An initial screening visit will occur to ensure subjects meet the inclusion criteria. This visit will include a physical exam and medical history, baseline EKG, ophthalmologic exam, baseline laboratory tests including a comprehensive metabolic panel and a complete blood count, and a clinical evaluation to ensure the patient has no factors that would render them ineligible for the study. Subjects will be required to give information regarding their medical history and melanoma treatment course.

Subjects will undergo screening procedures, including documentation of a medical history, patient demographics, vital signs, and ECOG performance status. Labs drawn will include CBC, chemistry, and coagulation profile. Archival tumor biopsy samples should be obtained from tissue available from any time prior to signing consent for this trial, focusing on samples since last treatment regimen until signing consent for this trial. Pre-treatment tumor biopsy will be performed prior to treatment administration during the screening period. A Pregnancy test will be performed on all women of childbearing potential. Baseline EKG and ECHO screening will be performed. Subjects will be asked to identify all concomitant medications they are or will be taking during the time of the study. Baseline imaging with a full body PET-CT or CT scans of the chest, abdomen, pelvis and areas of disease, along with brain MRI must be completed within 4 weeks prior to study enrollment.

6.2 Visit 2, 4

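### No LVEF measurement is scheduled inside the 42-day DLT window, so asymptomatic LVEF falls that count as DLTs would not be systematically detected before the RP2D is chosen

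*Combined protocol and SAP*

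**What the plan says.** **Decision window.** Section 3.1 has six patients treated at cohort 1 and "monitored for DLTs for 6 weeks (which is two treatment cycles (42 days". The rule is that "if none or one subject experiences a DLT, then dose cohort 1 will be considered the RP2D"; two or more DLTs in six lead to de-escalation. Section 3.5 repeats the period: the final MTD/RP2D is guided by drug-related side effects and "dose de-escalations occurring within 6 weeks (two cycles".

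**Role of LVEF.** Section 1.6.3 does not name LVEF, but it counts as a DLT any toxicity that requires permanent discontinuation of either drug. Table 1 (Section 1.6.1.2.1) requires permanent discontinuation of trametinib for, among other cardiac events, "Absolute decrease in LVEF of greater than 20% from baseline that is below LLN". It requires the same for a fall of 10% or more to below LLN that has not returned to normal after four weeks off drug. Once cohort 1 has failed, Section 3.1 uses LVEF to choose the next cohort: "Dose reduction to -1A or -2A is specifically for toxicity related to trametinib, LVEF reduction, RPED, pneumonitis and LFT abnormalities".

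**Measurement of LVEF.** Section 6.1 gives the baseline: "Baseline EKG and ECHO screening will be performed". In the Section 6.7 schedule, the only other ECHO/MUGA mark is in the column headed "Every 12 weeks or sooner, at the discretion of the physician". Footnote 15 repeats it: "ECHO/MUGA should be performed every 12 weeks, or at the discretion of the physician". Cycle 1, Cycle 2, the additional cycles and the end-of-treatment visit carry no ECHO/MUGA mark.

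**The concern.** The protocol makes LVEF an input to the run-in decision, both as a possible DLT and as a guide to which de-escalated cohort follows, but schedules no LVEF reading before that decision falls due. A site that follows the schedule exactly will have a baseline value for each of the six patients and no on-treatment value by day 42.

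The DLT-level fall above 20% carries no symptom requirement, and the milder row of Table 1 is expressly asymptomatic. The scheduled examinations, vital signs and EKG do not measure LVEF. Other toxicities in the same -1A/-2A list are treated differently: hepatic chemistry and an ophthalmoscope examination are scheduled on day 1 of every cycle.

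At stake is the primary phase Ib objective. Cohort 1 could be declared the RP2D, and phase II opened, with LVEF safety unassessed on treatment for a combination on which the protocol says no data exist.

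**Working it through.** **1. The plan's own figure.** Two 21-day cycles: 2 × 21 = 42 days; six weeks: 6 × 7 = 42 days. The stated window reproduces.

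**2. When the first scheduled on-treatment scan falls.** Footnote 15 does not say when its 12 weeks start.

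- From first dose: 12 × 7 = day 84, which is 84/42 = 2.0 times the window.
- From the screening scan, which can be up to 28 days before first dose (Section 6, Screening): 84 − 28 = day 56 at the earliest, so days 56 to 84, or 1.33 to 2.0 times the window. Allowing the 2-day visit tolerance gives day 54.

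On every reading the scan comes after day 42.

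**3. The four-week non-recovery route.** A fall of 10% or more becomes a discontinuation, and so a DLT, only after four weeks without recovery. To complete that inside the window, the fall must be found by day 42 − 28 = 14. A fall first found on day 84 would resolve on day 84 + 28 = 112 (week 16).

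**4. Effect on the decision.** Let q be the rate of other DLTs and l the rate of DLT-level LVEF falls within the window, taken as independent. The documents give neither. The only related figure is the 7% decrease in ejection fraction on single-agent trametinib (Section 1.4.2). It covers any degree and any time, in a dose-escalation trial that went above 2 mg, so 7% serves as an upper end for l.

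Per-patient DLT probability if LVEF events are seen: p = 1 − (1 − q)(1 − l). If unseen: p = q.

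P(cohort 1 accepted) = P(0 or 1 DLT in 6) = (1 − p)^6 + 6p(1 − p)^5.

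For q = 0.10, unseen: 0.9^6 + 6(0.10)(0.9^5) = 0.531 + 0.354 = 0.886. For q = 0.10 and l = 0.03, p = 1 − 0.90 × 0.97 = 0.127, and the result is 0.443 + 0.386 = 0.829.

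| q (assumed) | unseen | seen, l = 1% | seen, l = 3% | seen, l = 7% |
|---|---|---|---|---|
| 0.10 | 0.886 | 0.868 | 0.829 | 0.746 |
| 0.20 | 0.655 | 0.636 | 0.597 | 0.520 |
| 0.30 | 0.420 | 0.405 | 0.376 | 0.321 |

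The unseen column assumes that no discretionary scan finds anything; the seen columns assume that every event is found. Practice would lie between.

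**5. LVEF events alone.** At l = 7%, P(at least one in six) = 1 − 0.93^6 = 0.353, but the rule needs two DLTs: P(at least two in six) = 1 − 0.93^6 − 6(0.07)(0.93^5) = 0.061.

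**The case against.** Several points on the other side stand and limit what can be said.

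- **Discretionary scans.** A reader might infer that asymptomatic falls cannot enter the RP2D decision. The documents do not support that: both the column heading and footnote 15 allow earlier imaging, and a qualifying fall found by day 42 would count. Clinical visits could also prompt a scan, although they are weak at finding silent falls. The gap is one of systematic detection.
- **LVEF and cohort -1A.** It is tempting to read LVEF reduction as itself a DLT, or as enough to open -1A. Section 1.6.3 does not name it. It qualifies only through permanent discontinuation, an interruption of more than four weeks, or a grade 3 or higher nonhematologic toxicity. A fall that recovers within four weeks is not a DLT by the first two routes. Section 3.1 uses LVEF only to route between cohorts once two or more of six patients have had a DLT.
- **Size.** The 0.353 in step 5 invites the reading that the run-in has a one-in-three chance of going wrong. It counts one event of any degree at any time, whereas the rule needs two DLTs.
- **Slow accrual and other reviews.** At the NYU goal of 10 patients a year (Section 4.4.1), evenly spaced at one per 5.2 weeks, the sixth patient starts at week 5 × 5.2 = 26 and reaches day 42 at week 32. The first four would have passed their own week 12 by then, if still on treatment. The DSMC reviews safety quarterly and at cohort activation, and there is a toxicity hold after 20 patients.

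The last point softens the consequence but does not close the gap. Findings after six weeks are outside the DLT count that Sections 3.1 and 3.5 define, and the 20-patient hold follows the choice of RP2D. Reaching week 12 on treatment is not assured either. With the single-agent MEK inhibitor median PFS values in Section 7.2 (2.8 and 2 months), and assuming exponential PFS, the proportions progression-free at day 84 (2.76 months) are 0.5^(2.76/2.8) = 0.50 and 0.5^(2.76/2) = 0.38.

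**Conclusion.** The concern holds as a gap in ascertainment. Certain LVEF falls are DLTs through Table 1, the RP2D decision rests on 42 days, and no LVEF measurement is scheduled between first dose and day 42. The timing conclusion needs no assumption about footnote 15's starting point. Whether the first scan comes at exactly twice the window does: that is true only if the clock starts at first dose.

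The effect on the decision rule is modest. With other DLTs at an assumed 10%, unseen LVEF DLTs raise the chance of accepting cohort 1 by 0.018 at an LVEF-DLT rate of 1%, 0.057 at 3% and 0.140 at 7%. These figures rest on assumed rates, independence, and complete detection against none. The documents give no rate of DLT-level LVEF falls for either drug or the combination.

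The gap still merits correction, because it concerns a cardiac toxicity that the protocol itself singles out and it can be closed cheaply.

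**What to change.** For phase Ib, reconcile Table 1 (Section 1.6.1.2.1), Section 1.6.3, Sections 3.1 and 3.5, and the Section 6.7 schedule with footnote 15. The timing of the LVEF assessment already scheduled and the period on which the RP2D decision rests should agree, so that on-treatment LVEF data are available when the decision is made. State when the 12-week clock starts. How the passages are aligned is for the sponsor to choose; no cardiac schedule or DLT rule is proposed here.

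The cost is either one existing scan retimed per phase Ib patient, or a delay in the decision of at most about 84 − 42 = 42 days (six weeks) after the last run-in patient's day 42. Neither adds a procedure. If the decision is to wait for the existing reading, the text should also say how patients who stop treatment before it are handled, since the end-of-treatment visit carries no ECHO/MUGA mark.

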7.1 Sample Size Determination

For Phase 1b:

No data are available for the combination of CDX-3379 (ERBB3 antibody) and trametinib. Six subjects will be enrolled at an initial dose level – a safety run-in - and monitored for DLTs. In these six subjects, if none or one subject experiences a DLT, then dose cohort 1 will be considered the RP2D, and phase II of the clinical trial will proceed. If two or more of the six subjects experience DLT, we will consider the initial dose cohort beyond the MTD and we will enroll six more subjects on a de-escalated cohort, based on toxicity pattern observed attributed to a particular drug (Cohort -1A or -1B). In this new dose cohort, if none or one subject experiences a DLT, then the study will open to full enrollment on the Phase II portion of the trial. If two or more of these additional six subjects experience DLT, we will then enroll six additional subjects at an additional dose de-escalation cohort -2, to be determined by sponsor (NYUL Health) and DSMC), again based on toxicity pattern observed and drug attribution. If two or more subjects experience DLT at this new dose cohort, then the trial will be terminated.

For Phase 2: There are two Arms - Arm A (*NRAS* mutant melanoma participants) and Arm B (WT melanoma participants). This is the first part of a Simon Minimax design. Each Arm will initially enroll 19 patients. If there are two or fewer responses, the specific cohort will be stopped. Otherwise, the study will be amended to enroll a total of 36 patients to each approved Arm/cohort (an additional 17 patients per arm). If a true response rate is 0.20, we will have a probability of 0.46 of stopping early and a probability of 0.90 of deciding that the treatment is useful.

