Diagnosis and Main Inclusion Criteria	Unresectable Stage III and Stage IV melanoma who are positive for NRAS mutation or who are BRAF/NRAS WT and failed or are ineligible for standard treatment options
Study Product, Dose, Route, Regimen	CDX-3379 – ERBB3 human monoclonal antibody: 15mg/kg IV every three weeks Trametinib (Mekinist®) – MEK inhibitor: 2 mg PO daily

CONFIDENTIAL

Duration of administration	CDX-3379 infusion every three weeks and trametinib orally daily until disease progression, intolerable side effects, patient choice, or study closure
Reference therapy	
Phase 2 results of response rates will be compared to results from the NEMO trial for NRAS mutant melanoma – single agent MEK inhibitor (binimetinib) compared to DTIC – and WT melanoma to results from a phase I trial of trametinib in WT melanoma.
 
For Phase 2 exploratory objectives, PFS can be compared where PFS was 2.8 months for trametinib compared to 1.5 months for DTIC in NRAS mutant melanoma and PFS was 2 months for trametinib in WT melanoma.

Statistical Methodology	
Phase 1b: Safety run in of the combination of CDX-3379 and trametinib and monitored for DLTs. If DLT occurs in 2 or more participants, then de-escalated cohorts will be evaluated. Six to 18 evaluable participants will be treated to identify the MTD/RP2D prior to advancing to phase 2.
 
Phase 2: There are two Arms of the study – Arm A: NRAS mutant melanoma patients, and Arm B: WT melanoma patients. This is the first part of a Simon Minimax design. Each Arm will initially enroll 19 patients. If, after the 19 patients in each cohort, there are two or fewer responses, the cohort will be stopped. Otherwise, the study will be amended to accrue a total of 36 to each arm (an additional 17 participants per arm). If a true response rate is 0.20, we will have a probability of 0.46 of stopping early and a probability of 0.90 of deciding that the treatment is useful.

CONFIDENTIAL

1 Introduction

This document is a protocol for a human research study. This study is to be conducted in accordance with US government research regulations, and applicable international standards of Good Clinical Practice, and institutional research policies and procedures.

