7.2 Statistical Methods

Data collection will begin from time of enrollment and subjects will be followed until death (PFS and OS endpoints). If subjects are still alive, they will be censored at the time of evaluation. We will first investigate the association between biomarker expression and disease characteristics using t-test, ANOVA, or Chi-squared tests. We will then investigate the association between biomarker expression and PFS and OS using Kaplan-Meier approach and log rank test where biomarker expression is dichotomized. We may also use Cox proportional models to assess the association between biomarkers and outcome with adjustment for potential confounders such as disease characteristics. Biomarkers measured pre-, on-and post-treatment will be examined and are mainly exploratory at this time. Future tests will be derived from these results. For phase 2, the primary efficacy endpoint, response rate, will be compared with the historically reported response rate for the single agent trametinib in *NRAS* mutant and *BRAF/NRAS* WT melanoma. For secondary endpoints, we will estimate median PFS, OS and 95% CI using the Kaplan-Meier approach. In *NRAS* mutant melanoma patients treated with single agent MEK inhibitor, response rate was 15% and median PFS was 2.8 months¹⁵, and in *BRAF/NRAS* WT melanoma

CONFIDENTIAL

patients treated with single agent MEK inhibitor, response rate was 10% and median PFS was 2 months⁷

Assuming a true response rate of 0.20, Simon's two-stage Minimax design will test the null hypothesis that $RR \leq 0.20$; the sample size of 36 patients provides an alpha level of 0.10 and power of 0.80. Nineteen patients will be enrolled to the *NRAS* mutant arm of the study and 19 patients will be enrolled to the BRAF/*NRAS* WT arm of the study in the phase 2. If at least 3 patients respond (PR or better) out of 19 evaluable patients, then the study will be amended to enroll an additional 17 patients (for a total of 36 evaluable patients). If the Simon two-stage Minimax design is fully completed, a minimum of 10 patients must demonstrate a response (PR or better) to reject the null hypothesis.

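### The stage-1 futility boundary is printed as both two-or-fewer and three-or-fewer responses of 19, and the stated 0.46 early-stopping probability fits only three-or-fewer

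*Combined protocol and SAP*

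**What the plan says.** Phase 2 has two arms, NRAS mutant and BRAF/NRAS wild type. Each enrols 19 patients as the first stage of a Simon minimax design, and an arm that passes would be expanded by amendment to 36. The stage-1 rule appears in four places:

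- Study Summary, Statistical Methodology: "If, after the 19 patients in each cohort, there are two or fewer responses, the cohort will be stopped".
- Section 3.1, General Design: "If there are three or fewer responses, then accrual to that cohort will be stopped".
- Section 7.1, Sample Size Determination: "If there are two or fewer responses, the specific cohort will be stopped".
- Section 7.2, Statistical Methods: "If at least 3 patients respond (PR or better) out of 19 evaluable patients, then the study will be amended" to add 17 patients. This is the same as stopping at 2 or fewer.

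Section 7.1 also gives the operating characteristic: "If a true response rate is 0.20, we will have a probability of 0.46 of stopping early". The Study Summary repeats the 0.46. In both places it stands beside the two-or-fewer rule.

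**The concern.** Three places stop at 2 or fewer and one stops at 3 or fewer, so 3 responders of 19 leads to opposite actions. Counting sections does not settle it, because the probability quoted next to the majority wording looks far too high for that boundary.

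The protocol executes only stage 1, and stage 2 needs an amendment. The boundary is therefore the one formal efficacy go/no-go rule that will be applied, and it is applied to response rate, a primary phase 2 endpoint. If an arm finishes on 3 responders, the choice of rule would be made with the responses already known, in an open-label study, with 17 further patients in that arm depending on it. If the two-or-fewer wording is followed, the protection against continuing with a treatment whose true rate is 0.20 is about half of what is claimed.

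**Working it through.** **Inputs.** Stage-1 size n1 = 19, total n = 36, true rate 0.20, stated stopping probability 0.46 (section 7.1). Boundaries r1 = 2 (Study Summary, 7.1, 7.2) and r1 = 3 (section 3.1). Historical single-agent response rates 0.15 for NRAS mutant and 0.10 for wild type, null rate 0.20, alpha 0.10 (section 7.2).

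**Step 1: reproduce the stated 0.46.** P(stop) = P(X ≤ r1) with X ~ Binomial(19, 0.20) and P(X = k) = C(19, k) × 0.20^k × 0.80^(19−k).

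| k | P(X = k) | P(X ≤ k) |
|---|---|---|
| 0 | 0.0144 | 0.0144 |
| 1 | 19 × 0.20 × 0.80^18 = 0.0685 | 0.0829 |
| 2 | 171 × 0.04 × 0.80^17 = 0.1540 | 0.2369 |
| 3 | 969 × 0.008 × 0.80^16 = 0.2182 | 0.4551 |

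P(X ≤ 4) is 0.6733. Only r1 = 3 rounds to 0.46. The rule printed beside the figure gives 0.24, a shortfall of 22 points.

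**Step 2: how often the two rules disagree.** They differ only when X = 3.

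| True rate | P(X ≤ 2) | P(X ≤ 3) | P(X = 3) |
|---|---|---|---|
| 0.10 | 0.705 | 0.885 | 0.180 |
| 0.15 | 0.441 | 0.684 | 0.243 |
| 0.20 | 0.237 | 0.455 | 0.218 |
| 0.30 | 0.046 | 0.133 | 0.087 |
| 0.40 | 0.006 | 0.023 | 0.018 |

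If each arm merely matched its historical rate (0.15 and 0.10) and the arms were independent, the chance that at least one arm ended on exactly 3 would be 1 − (1 − 0.243)(1 − 0.180) = 0.38.

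**Step 3: expected size per arm at a true rate of 0.20, if stage 2 follows.** EN = 19 + 17 × (1 − P(stop)).

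- r1 = 2: 19 + 17 × 0.7631 = 31.97
- r1 = 3: 19 + 17 × 0.5449 = 28.26

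**Step 4: cross-check on the intended design.** The plan states no alternative rate. Assume 0.40. An exhaustive minimax search with null 0.20, alternative 0.40, alpha 0.10 and power 0.90 returns stop at ≤ 3 of 19 and reject at ≥ 11 of 36, with early stopping 0.4551, alpha 0.0861 and power 0.9024. This matches the plan's 19, 36, 0.46 and 0.90 together. With power 0.80, the value in section 7.2, the search returns 2/14 and 7/24, which matches neither sample size.

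**Step 5: price of three or fewer in place of two or fewer** (overall power).

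| Success rule | True rate | r1 = 2 | r1 = 3 | Loss |
|---|---|---|---|---|
| ≥ 10 of 36 (section 7.2) | 0.40 | 0.9533 | 0.9436 | 1.0 point |
| ≥ 10 of 36 | 0.35 | 0.8583 | 0.8422 | 1.6 points |
| ≥ 11 of 36 (from step 4) | 0.40 | 0.9086 | 0.9024 | 0.6 points |

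**The case against.** The strongest reply is that this is a slip in one section, with three places agreeing on two or fewer, and that no expansion can happen without an amendment, when someone would notice. The amendment does give a checkpoint. It does not resolve the conflict, because the majority wording is the one contradicted by the probability printed next to it, and by then the responses would be known. The later, more detailed SAP promised in section 7.2 is due only before database lock, which may come after the stage-1 decision.

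Several limits do stand:

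- The 0.46 excludes two or fewer only at the stated rate of 0.20. Two or fewer would give 0.44 at 0.15 and would reach 0.46 at about 0.146. Both places that quote 0.46 tie it to 0.20.
- The one-in-five frequency applies at rates of 0.10 to 0.20. At 0.40 the disputed result has probability 0.018.
- The design in step 4 rests on an assumed alternative of 0.40 and on power 0.90 rather than 0.80. Its final cutoff of 11 differs from the minimum of 10 in section 7.2. It supports three or fewer but does not prove it.
- Stopping at three or fewer also closes more arms with a moderately active treatment: 0.133 against 0.046 at a true rate of 0.30.

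None of these removes the contradiction or makes 0.46 correct for the rule beside it.

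**Conclusion.** The concern holds and must be fixed. The plan contains two incompatible stage-1 boundaries with no order of precedence. At the stated true rate of 0.20 the early-stopping probability is 0.237 under two or fewer and 0.455 under three or fewer, so the printed 0.46 is wrong for the rule in the Study Summary and section 7.1 and right for the rule in section 3.1. These results need only n1 = 19, the rate of 0.20 and independent binomial responses; they do not depend on any assumed alternative. The inference that three or fewer was the intended boundary does lean on the assumed 0.40, and the expected sizes of 32.0 and 28.3 assume that stage 2 is opened.

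**What to change.** Use one stage-1 boundary in all four places. The choice that agrees with the stated 0.46 is to stop an arm at 3 or fewer responses of 19 and continue at 4 or more. The Study Summary and section 7.1 would then read three or fewer, section 7.2 would require at least 4 responders, and section 3.1 would stand. If the sponsor prefers two or fewer, section 3.1 should change to match, and the 0.46 in the Study Summary and section 7.1 should become 0.24.

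The same amendment should state the null rate, alternative rate, alpha, power and both boundaries together. The stage-1 edit alone leaves related conflicts. Success at 10 of 36 gives an alpha of 0.158 with three or fewer and 0.166 with two or fewer, against the stated 0.10. Power is 0.90 in section 7.1 but 0.80 in section 7.2, and the 0.90 is attached to a true rate of 0.20, which section 7.2 makes the null.

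The cost is wording only, with no extra stage-1 patients. Choosing three or fewer costs up to about 1 point of power at a true rate of 0.40 and 1.6 points at 0.35 under the stated 10-of-36 rule. The decision should be made before either arm's stage-1 responses are reviewed.
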